Other adverse events (toxicity) will be listed and summarized overall and by dose level. Adverse events will also be listed by severity, seriousness, and by system organ class. The number and percentage of subjects who experience AEs will be presented in tabular and/or graphical format and summarized descriptively, where appropriate. No formal statistical comparison between the dose levels or PD-L1 will be performed. AEs will be presented with and without regard to causality based on the investigator's judgment. The frequency of overall toxicity, categorized by toxicity grades 1 through 5, will be described. Additional summaries will be provided for AEs that are observed with higher frequency.

Efficacy Analyses:

The primary and secondary efficacy analyses will include all enrolled patients who have received at least one dose of durvalumab, underwent resection and who do not have EGFR mutant tumors (*efficacy population*).

Primary Efficacy Endpoint

The effectiveness of sirolimus followed by durvalumab will be assessed by complete pathologic response rate in the *efficacy population*. If the null hypothesis is rejected then this is evidence that the response rate exceeds 10% when sirolimus followed by durvalumab is given before resection. The one-sided 95% confidence interval (CI) for complete pathologic response will be reported. Exact binomial test will be used to compare the estimated complete pathologic response rate to the historical reference.

Secondary Efficacy Endpoints

The complete pathologic response rates for PDL-1 negative and PDL-1 positive patients in the *efficacy population* will be presented separately.

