	Screening	Sirolimus	Durvalumab C1	Durvalumab C2	Pre- surgery	Surgery	Study DC	Follow- up	For details see Section	
Week	-4 to 0	0	3	6	8-9		Post Surgery 30 +/- 7 days	Every 3 months for 2 years		
Day	-28 to 0	1-21	22 +/- 3 days^a	43 +/- 3 days^a	57-64 +/- 10 days					
Tumor biopsy (newly acquired/fresh if amenable to core biopsy)	X								Error! Reference source not found. Error! Reference source not found.	
Tumor biopsy (archival, required for diagnosis and PD-L1 assessment)	X								Error! Reference source not found.	
Fresh tumor and lymph node samples for immunologic analysis						X				
Efficacy evaluations										

Clinical Study Protocol

Drug Substance Sirolimus (Rapamune)

Study Number **19-20015**

Edition Number: **4**

Date: **11 February 2022**

	Screening	Sirolimus	Durvalumab C1		Durvalumab C2		Pre- surgery	Surgery	Study DC	Follow- up	For details see Section	
Week	-4 to 0	0	3		6		8-9		Post Surgery 30 +/- 7 days	Every 3 months for 2 years		
Day	-28 to 0	1-21	22 +/- 3 days^a		43 +/- 3 days^a		57-64 +/- 10 days					
Tumor evaluation (CT or MRI) (RECIST 1.1) ¹ within 6 weeks of C1D1	X ^b						X				Error! Referen ce source not found.	
Pathologic response assessment								X				

^a If cycle 2 day 1 visit is delayed, all subsequent visits will be delayed accordingly

^b Informed consent of study procedures and tumor biopsy sample may be obtained prior to the 28-day screening window, if necessary, in order to permit tumor biopsy sample acquisition and analysis prior to randomization. The collection of tumor biopsies at the time of progression prior to retreatment is mandated; the Investigator must consult with the Study Physician if such sampling is not feasible. If laboratory or imaging procedures were performed for alternate reasons prior to signing consent, these can be used for screening purposes with consent of the patient. However, all screening laboratory and imaging results must have been obtained within 28 days of study assignment.

^c Body weight is recorded at each visit along with vital signs

^d Any clinically significant abnormalities detected require triplicate ECG results.

^e Serum or plasma clinical chemistry (including LFT monitoring) and hematology may be performed more frequently if clinically indicated.

^f If screening clinical chemistry and haematology assessments are performed within 3 days prior to Day 1 (first infusion day), they do not need to be repeated at Day 1.

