4. PATIENT SELECTION

4.1 Inclusion criteria

For inclusion in the study patients must fulfill all of the following criteria:

1. Patients with pathologically documented NSCLC who are deemed to be candidates for definitive surgery: Stage will be categorized based on 8th edition of American Joint Committee on Cancer (AJCC) Non-small cell Lung Cancer Staging system; see Appendix 3.
2. Capable of giving signed informed consent which includes compliance with the requirements and restrictions listed in the informed consent form (ICF) and in this protocol. Written informed consent and any locally required authorization (eg, Health Insurance Portability and Accountability Act in the US) obtained from the patient/legal representative prior to performing any protocol-related procedures, including screening evaluations.
3. Age ≥ 18 years at time of study entry.
4. Eastern Cooperative Oncology Group (ECOG) performance status of 0 or 1
5. Life expectancy of ≥ 26 weeks
6. Body weight >30 kg
7. Adequate normal organ and marrow function as defined below:
 - Haemoglobin ≥ 9.0 g/dL
 - Absolute neutrophil count (ANC) $1.5 \times 10^9/L$ (≥ 1500 per mm 3)
 - Platelet count $\geq 100 \times 10^9/L$ ($\geq 100,000$ per mm 3)
 - Serum bilirubin $\leq 1.5 \times$ institutional upper limit of normal (ULN).
 - AST (SGOT)/ALT (SGPT) $\leq 2.5 \times$ institutional upper limit of normal unless liver metastases are present, in which case it must be ≤ 5 x ULN
 - Measured creatinine clearance (CL) >40 mL/min or Calculated creatinine CL >40 mL/min by the Cockcroft-Gault formula (Cockcroft and Gault 1976) or by 24-hour urine collection for determination of creatinine clearance:

Males:

$$\text{Creatinine CL} = \frac{\text{Weight (kg)} \times (140 - \text{Age})}{72 \times \text{serum creatinine (mg/dL)}}$$

Females:

$$\text{Creatinine CL} = \frac{\text{Weight (kg)} \times (140 - \text{Age})}{72 \times \text{serum creatinine (mg/dL)}} \times 0.85$$

8. Evidence of post-menopausal status or negative urinary or serum pregnancy test for female pre-menopausal patients. Women will be considered post-menopausal if they have been amenorrheic for 12 months without an alternative medical cause. The following age-specific requirements apply:

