4.2 Exclusion criteria

Patients should not enter the study if any of the following exclusion criteria are fulfilled:

1. Patients who have had prior therapy for lung cancer including chemotherapy, hormonal therapy, or radiotherapy.
2. Concurrent enrolment in another clinical study, unless it is an observational (non-interventional) clinical study
3. Prior treatment with anti-PD-1, anti-PDL-1, including durvalumab other PD-1/PDL-1 pathway targeting agents, or mTOR inhibition.
4. History of allogenic organ transplantation.
5. Active or prior documented autoimmune or inflammatory disorders (including inflammatory bowel disease [e.g., colitis or Crohn's disease], systemic lupus erythematosus, Sarcoidosis syndrome, or Wegener syndrome [granulomatosis with polyangiitis, Graves' disease, rheumatoid arthritis, hypophysitis, uveitis, etc]). The following are exceptions to this criterion:
 - a. Patients with vitiligo or alopecia
 - b. Patients with hypothyroidism (e.g., following Hashimoto syndrome) stable on hormone replacement
 - c. Any chronic skin condition that does not require systemic therapy
 - d. Patients without active disease in the last 5 years may be included but only after consultation with the study physician
 - e. Patients with celiac disease controlled by diet alone
6. Uncontrolled intercurrent illness, including but not limited to, ongoing or active infection, symptomatic congestive heart failure, uncontrolled hypertension, unstable angina pectoris, cardiac arrhythmia, interstitial lung disease, serious chronic gastrointestinal conditions associated with diarrhea, or psychiatric illness/social situations that would limit compliance with study requirement, substantially increase risk of incurring AEs or compromise the ability of the patient to give written informed consent
7. History of another primary malignancy except for

- a. Malignancy treated with curative intent and with no known active disease ≥ 5 years before the first dose of IP and of low potential risk for recurrence
- b. Adequately treated non-melanoma skin cancer or lentigo maligna without evidence of disease
- c. Adequately treated carcinoma in situ without evidence of disease

8. QT interval corrected for heart rate using Fridericia's formula (QTcF) ≥ 470 ms. Patient safety and the cardiac SKG should be consulted as needed.

9. History of active primary immunodeficiency

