- When submitting sample to for PD-L1 testing the recommendation is to ship the block in order for sectioning to occur at the laboratory. Blocks should be shipped - containing enough material to be provided to allow a minimum of 5, and preferably 10, sections to be cut (each 4-micron thick) to be used for PD-L1 testing.

Sectioning instructions

- Where it is not possible or indicated to ship the block to laboratory for PD-L1 testing, unstained slides should be prepared from the paraffin-embedded tumor sample block as described below:
 - A minimum of 5-10 x 4 micron (μ m) thick, unstained sections should be provided for PD-L1 testing
 - A new disposable microtome blade must be used for each block to prevent contamination between patient samples
 - Slides are stable under these conditions for 6 months.

Clinical Study Protocol

Investigational Drug Substance: MEDI4736 Sirolimus (Rapamune)

Study Number **19-20015**

Edition Number: **4**

Date: **11 February 2022**

- Apply one section per slide to positively-charged Superfrost glass slides
- The sections should be dried overnight between room temperature and 37°C. Do not dry sections at temperatures above 37°C.

Sections should be stored at ambient temperature and protected from light until use or shipment to testing lab by courier at ambient temperature. It is recommended that slides are cut freshly prior to PD-L1 testing and they are used within 90 days of being cut to obtain PD-L1 status.

Next Generation Sequencing of the tumor Either an internal or external validated platform to test for a wide panel of genes including those known to have prognostic or predictive impact on lung cancer outcomes will be tested as per standard institutional protocol.

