Deuterium enrichment in the body water can be determined by collection of saliva, urine or blood samples. CD8 T cells, CD4 T cells and regulatory T cell populations will be sorted from the blood and post-surgical tissues at the Emory flow cytometry core, cell pellets frozen and sent to [name]'s laboratory for DNA extraction and analysis of 2H enrichment. Specifically, we will analyze how much deuterium incorporation has occurred in various sorted subsets to measure the level of proliferation in the cell types in the window of deuterium incorporation.

Sample Prioritization

Pre- and Post-Treatment FFPE Biopsy Samples

1. Pathology analyses
2. PD-L1 IHC analysis
3. Multiplex IF analysis
4. Banking for additional non-protocol-specified exploratory analyses

Pre-Treatment Fresh Frozen Biopsy Samples

1. RNA isolation and sequencing
2. Back-up for RNA and banking for additional non-protocol-specified exploratory analyses

Post-Treatment Fresh Frozen Biopsy Samples

1. RNA sequencing
2. DNA extraction and WES

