11.1.2 Efficacy analysis set

The primary and secondary efficacy analyses will include all enrolled patients who have received at least one dose of durvalumab, underwent resection and who do not have EGFR mutant tumors (efficacy population).

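### EGFR status removes treated patients from the efficacy set, but the plan fixes neither the specimen nor the date of the test, and the 16/31 rule does not allow for the loss

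*Combined protocol and SAP*

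**What the plan says.** **Who enters.** Section 4.1 admits "Patients with pathologically documented NSCLC who are deemed to be candidates for definitive surgery". Neither 4.1 nor the 18 exclusion criteria of 4.2, introduced by "Patients should not enter the study if any of the following exclusion criteria are fulfilled", mention EGFR. The screening list in 8.1.1 and the Schedule of Study Assessments contain no EGFR or sequencing test.

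**Who is analyzed.** The synopsis and 11.1.2 give the same set: "The primary and secondary efficacy analyses will include all enrolled patients who have received at least one dose of durvalumab", had resection, and "who do not have EGFR mutant tumors (efficacy population". Section 11.2.2 runs the exact binomial test against the historical reference in this set.

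**How EGFR is found.** The only passage on a gene panel, at the end of 8.2.1, says that the genes "will be tested as per standard institutional protocol". It does not name EGFR, a specimen or a time point. In the sample priorities of 8.2.2, "DNA extraction and WES" stands only under post-treatment frozen tissue; the pre-treatment frozen list names RNA. The schedule requires pre-treatment tissue for other purposes: "Tumor biopsy (archival, required for diagnosis and PD-L1 assessment".

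**Who is counted.** Under 4.4, only withdrawal of consent before durvalumab leads to replacement. Section 11.3 continues with at least 2 pathologic complete responses (pCR) in 16 patients and calls the regimen promising with 6 or more in 31. It states 80% power at one-sided alpha 0.10 for 25% against 10%.

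**The concern.** EGFR status is a baseline trait, but here it sets the denominator of the primary analysis and may be learned after the primary outcome. The trial is open-label and single-arm. No rule fixes the set before pathology is read, and none covers unknown EGFR status.

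The direction of a possible error is known. If the resection specimen were the source, a non-responder's specimen would have tumor to sequence, while a pCR specimen might have none. A mutant non-responder would leave the set and a mutant responder would stay. The reported pCR rate and its lower confidence bound would rise, and the exact p-value would fall.

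A second problem does not depend on timing. EGFR-mutant patients take up places among the 16 and 31 without replacement, while the efficacy set leaves them out. The stated power assumes that all 31 can contribute a counted response.

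**Working it through.** **Inputs.** From 11.3: null rate 0.10, alternative 0.25, 2 of 16, then 6 of 31, alpha 0.10. From 4.4: no replacement. The documents give no EGFR-mutant share m, so 5 to 20% is an assumption shown as a range.

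**1. The plan's own figure.** P(success) = Σ over x = 2 to 16 of P(Bin(16, p) = x) × P(Bin(15, p) ≥ 6 − x).
- p = 0.10: 0.0788
- p = 0.25: 0.8053

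The stated alpha limit and power are reproduced.

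**2. What removing non-responders does to the exact test.** Take 5 pCRs and p-value = P(Bin(n, 0.10) ≥ 5).

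| Removed | n | Rate | p |
|---|---|---|---|
| 0 | 31 | 16.1% | 0.193 |
| 1 | 30 | 16.7% | 0.175 |
| 4 | 27 | 18.5% | 0.127 |
| 5 | 26 | 19.2% | 0.112 |
| 6 | 25 | 20.0% | 0.098 |

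For n = 26 to 31 the test still needs 6 responses. Only the sixth removal lowers the requirement to 5.

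**3. Type I error under selective exclusion.** Assume that every responder stays, that each non-responder is removed with probability m and not replaced, that stage I needs 2 responses among 16 enrolled, and that the final exact test at 0.10 uses the remaining n. By step 2, nearly all the added error comes from trials with exactly 5 responses and at least 6 of 26 non-responders removed. At the null rate, 5 responses with stage I passed has probability Σ over x = 2 to 5 of P(Bin(16, 0.10) = x) × P(Bin(15, 0.10) = 5 − x) = 0.0937.

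| m | P(Bin(26, m) ≥ 6) | 0.0788 + 0.0937 × that | Full sum over all outcomes |
|---|---|---|---|
| 5% | 0.0015 | 0.0789 | 0.079 |
| 10% | 0.0399 | 0.0825 | 0.083 |
| 15% | 0.1850 | 0.0961 | 0.096 |
| 20% | 0.4225 | 0.1184 | 0.119 |

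If the removed non-responders were replaced until 16 and 31 were evaluable, which 4.4 does not provide for, the error would be 0.094, 0.112, 0.134 and 0.161.

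**4. Power when EGFR-mutant patients add no counted response.** Use the formula of step 1 at p = 0.25 and the same cut-offs, with 16 − k1 and 15 − k2 patients who can count.
- 3 patients (k1 = 1, k2 = 2): 0.721
- 4 patients (2, 2): 0.682
- 6 patients (3, 3): 0.604

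If the final test instead uses the reduced n, with status unrelated to response, power is 0.761, 0.721, 0.698 and 0.680 for m = 5, 10, 15 and 20%.

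**The case against.** **Baseline tissue is required.** A reader might infer that late exclusion can fall only on non-responders. The documents do not support that. The schedule requires a diagnostic biopsy, item 10 of 4.1 requires consent to a pre-treatment research biopsy, and 1.1.2 limits entry to patients with enough initial biopsy material for biomarkers. Section 8.2.5.1 also allows DNA analysis of pre-treatment cores as an option. A patient with a pCR can therefore be genotyped from baseline tissue. This objection stands: selection arises only if the resection is the source. What remains is that no text assigns the baseline tissue to EGFR status, so the plan permits either route.

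**The 5/31 to 5/25 example is not proof of bias.** The same change occurs if six mutant non-responders are identified from baseline tissue and set aside in advance. It also takes all six: one to five removals cross nothing, and the exact one-sided 95% lower bound for 5/25 is 8.2%, still below 10%. This stands. The measure of bias is step 3, not the example.

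**The go decision is a count.** Removing non-responders cannot produce a sixth pCR. Read literally, the rule in 11.3 is unaffected. The exposed results are the reported rate, its interval and the exact test of 11.2.2.

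**Safety for all, efficacy for some, is coherent.** Enrolling all resectable NSCLC while restricting efficacy to tumors without EGFR mutation is a legitimate choice. A reader might object that patients known not to count are being treated. The plan does not say that status is known before treatment, and these patients do count for the co-primary safety objective.

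**Conclusion.** The point holds in limited form. The plan lets a baseline trait be established after the outcome and then used to define the primary set. If that happened through the resection specimen alone, the error would favor the regimen. Its size is modest: the type I error stays within 0.10 up to an assumed share of 15% and reaches 0.119 at 20%. This rests on complete selectivity and no replacement. The documents do not show that selective exclusion will occur, nor that a literal 6-of-31 decision would be distorted.

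The mismatch of denominators needs no assumption about timing. With 3 to 6 EGFR-mutant patients among 31, also an assumption, the 80% power becomes 72% to 60% if the counts stay fixed. Sections 11.1.2 and 11.3 should be made to agree.

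**What to change.** **Sections 8.2.1 and 11.1.2.** Determine EGFR status from the required pre-treatment tissue only. Lock it before the resection specimen is read. Keep patients without a baseline result in the efficacy set. Report the pCR rate with EGFR-mutant patients included as a sensitivity analysis.

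**Section 11.3.** State whether 16 and 31 count enrolled or efficacy-evaluable patients, and restate the power to match. Make this change together with the first: step 3 shows that filling the evaluable places while EGFR is still read late would enlarge the error.

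**Cost.** This is wording, since sequencing is already planned. The result has to be timed against surgery. If the counts are of enrolled patients, the restated power may be below 80%; if they are of evaluable patients, total enrollment may exceed 31.

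**Not required.** Excluding EGFR-mutant patients at entry is the sponsor's choice. It would keep the stated design, but the sequencing turnaround could delay some starts.

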11.2 Methods of statistical analyses

The number of patients who enroll, discontinue, or complete the study will be summarized. Reasons for premature study withdrawal will be listed and summarized. Enrollment and major protocol deviations will be listed and evaluated for their potential effects on the interpretation of study results. Demographic information such as age and race will be tabulated. Descriptive statistics, including means, standard deviations, and ranges for continuous parameters, as well as percentages and frequencies for categorical parameters, will be presented. Adverse events, Grade 3/4 adverse events, and serious adverse events will be tabulated.

11.2.1 Safety analyses

After study complete, DLTs will be summarized and tabulated by type and grade. DLT rate will be calculated as proportion (Patients with DLT/Total patients) along with 95% confidence intervals using the Clopper-Pearson method. Chi-square test or Fisher's exact test will be used to compare the probability of DLT between the different other factors, such as PD-L1 status, , etc. respectively.

Other adverse events (toxicity) will be listed and summarized. Adverse events will also be listed by severity, seriousness, and by system organ class. The number and percentage of subjects who experience AEs will be presented in tabular and/or graphical format and summarized descriptively, where appropriate. AEs will be presented with and without regard to causality based on the investigator's judgment. The frequency of overall toxicity, categorized by toxicity grades 1 through 5, will be described. Additional summaries will be provided for AEs that are observed with higher frequency.

11.2.2 Efficacy analyses

Primary Efficacy Endpoint

The effectiveness of sirolimus followed by durvalumab will be assessed by complete pathologic response rate in the efficacy population. If the null hypothesis is rejected then this is evidence that the response rate exceeds 10% when sirolimus followed by durvalumab is given before resection. The one-sided 95% confidence interval (CI) for complete pathologic response will be reported. Exact binomial test will be used to compare the estimated complete pathologic response rate to the historical reference.

Secondary Efficacy Endpoints

The complete pathologic response rates for PDL-1 negative and PDL-1 positive patients in the *efficacy population* will be presented separately.

A comparison of both the *complete pathologic response* and investigator assessed response rates per RECIST v1.1 rates between the PD-L1 positive and PD-L1 negative groups will be performed by calculating the lower bound of a one-sided 80% CI for the difference, complete pathologic response for PDL-1 positive patients – complete pathologic response for PDL-1 negative patients. Chi-square test or Fisher's exact test will be used to compare the efficacy in term of response rate between the different groups stratified by other factors, respectively. Logistics regression model will be further employed to test the adjusted effect of each other factor on the response rate after adjusting for other clinical factors and demographic factors, respectively. Correlation of response will be performed for tumor mutation burden using spearman correlation coefficient and tested with Wald's test.

